HAWS; Haemoglobin Application to Wounds Study, a single-centre, controlled, prospective randomized trial

Version 6, dd 10July 2018

Chief Investigator's Statement of Ownership and Content.

I, [name], confirm that this protocol is my work and is owned by me. The protocol conforms with standards outlined in the Declaration of Helsinki 1964.

Name (PRINT): [name]

Signature:

Date: LATH SEP. 2018

RESEARCH PROTOCOL SUMMARY

TITLE:	Haemoglobin Application to Wounds Study, a single-centre, controlled, prospective, randomized trial of Granulox
	haemoglobin spray for adjuvant treatment of foot ulcers
Short title:	HAWS; Haemoglobin Application to Wounds Study
IRAS number	227421
Device description	Granulox® Medical device. Class III, CE 0482
	Indications: Granulox® is a spray for use on chronic wounds. Granulox® is an innovative medical device for the proposed treatment of chronic wounds, such as venous leg ulcer, arterial leg ulcer, mixed leg ulcer, foot ulcers, secondary healing of surgical wounds and pressure sores. Granulox® can also be used on sloughy and infected wounds. Each canister contains 12 ml of spray, sufficient for 30 wound treatments.
Study design	Single-centre, controlled, prospective randomized trial
Primary objective	To determine the efficacy of the Granulox spray as an adjuvant therapy for foot ulcers at 3, 6, 9 and 12 weeks post-baseline - Healing rate (ulcer size; 12 weeks is endpoint for power calculation), as measured with surface area scoring grid
Secondary objectives	Clinical assessment at -2, 0, 3, 6, 9 and 12 weeks, and - PUSH ulcer size/grading score - Texas Univ grading score - Wound closure Safety of Granulox spray throughout trial duration, up to 12 weeks - Wound infection incidence; secondary interventions Patient-reported outcome measures at 0, 6 and 12 weeks - Patient mobility score (LifeSpace questionnaire) - Quality of life score (EQ-5D-5L and CWIQ) - Visual Analogue Score for pain associated with DFU Status of wound at week 18 - Healed, not healed, recurrence.
Patient population	A total of 60 participants, over the age of eighteen, with measurable foot ulcer, treated in clinic. Forty patients to have a DFU and further 20 patients to have nondiabetes related foot

	Indiana B. III in the second s
	ulcer. Participants must have the capacity to provide informed written consent and complete patient reported outcome measures.
	 30 Patient will receive treatment as usual (TaU) 30 Patients will receive TaU plus adjuvant Granulox application twice weekly.
	Randomisation will be stratified for diabetes diagnosis (yes/no) and ulcer size, with cut-off PUSH score of 6 and above, or 5 or less. Patients will first go through a two week screening period; those patients with a healing rate of > 50% in 2 weeks will not be eligible for the intervention period.
Sponsor	Cumbria Partnership NHS Foundation Trust
Manufacturer & research grant provider	SASTOMED GMBH, https://granulox.de/en/sastomed contact: [name], EngelsConsult
	[name] [contact]; [contact] [contact]
Chief Investigator	[name] [name], GPwSI Research, [contact] or [name] [contact] Cumbria Partnership NHS Foundation Trust R&D Department, [name]
Co-investigators	[name] PhD, Science & Innovation Manager, [contact] or [name]; [contact] Cumbria Partnership NHS Foundation Trust R&D Department, [name]
	[name] Podiatry Lead Cumbria Partnership NHS Foundation Trust [name]
Organisation where research will take place	Cumbria Partnership NHS Foundation Trust Carleton Clinic R&D department [name]
	[contact]

Planned timeline	Recruitment start date (first patient, first visit) July 2017,
	Recruitment end date (last patient, first visit): 31 Jan 2019
	Trial end date: Apr 2019
Protocol version, date	Version 6, 10 July 2018

1.	Lay summary	6
2.	Introduction	6
3.	Investigational device	8
4.	Study hypothesis	9
4.1	Primary objective	9
4.2	Secondary objective	9
5.	Study protocol	9
5.1	Study design and timeline	9
5.2	Participant identification	10
5.3	Consent	11
5.4	Recruitment	11
5.5	Follow-up	12
5.6	Outcome measures	12
5.6.	1 Primary outcome measures	12
5.6.	2 Secondary outcome measures	12
6.	Subjects	13
6.1	Anticipated number of research subjects	13
6.1.	1 Randomisation	14
6.2	Eligibility criteria	14
6.2.	1 Inclusion criteria	14
6.2.	.2 Exclusion criteria	15
6.3	Early withdrawal of subjects	15
7.	Safety	15

7.1	Potential risks & benefits to study participants	15
7.2	Safety definitions	
7.3	Procedures for recording adverse events	
8.	Statistical consideration and data analysis plan	
8.1	Analysis of baseline characteristics	
8.2	Primary outcome statistics	
8.3	Secondary outcome statistics	.18
9. 1	Data handling and monitoring	.18
10.	Goverance of study	.19
10.1	Approvals	
10.2	Sponsor & Indemnity	19

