5.2 Participant identification and research setting

Participants will be recruited from podiatry clinics and all eligible patients will be invited to take part until the required numbers have been achieved. Identification will be by the podiatrists who are supporting the study. A screening form will be completed for potentially eligible patients to confirm that they indeed meet the trial criteria.

The podiatry team in West Cumbria will be supporting this study, and the study will take place in Whitehaven, Workington, Cockermouth and Wigton. All research activity and also treatment as usual (ie application of dressings) will take place in these clinic settings. Additional resource, paid for by the research grant for this study, means that there is sufficient capacity to treat study participants with the Granulox medical device. All podiatrists – 4 staff in total - will receive training on the use of the medical device by a representative of InFirst Healthcare.

To summarise, the podiatrists will:

- Identify potentially eligible patients and ask verbal consent for them beign approached about the study by a member of the R&D team
- Complete the incl/excl criteria part of the screening form
- Apart from treatment as usual activities (dressings, cleaning of wound, footwear advice), measure the wound size and complete the PUSH and Texas University score once a patient has consented to taking part (informed consent will be taken by members of R&D team, or one of the podiatrist so long as GCP training has been completed).

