5.6.2 Secondary outcome measures

This study also aims to record wound characteristics and patient-related outcomes measures, as well as safety endpoints.

- Size and characteristics of foot ulcer, determined with PUSH score (week -2, 0, 3, 6, 9, 12)
- Grading of foot ulcer, using Texas Univ grading score (week -2, 0, 3, 6, 9, 12).
- Wound closure status (week 0, 3, 6, 9, 12)
- Mobility score, as determined by LifeSpace questionnaire (week 0, 6, 12)

- Visual Analogue Pain score (week -2, 0, 3, 6, 9, 12)
- Quality of life score, determined with EQ5D-5L and Charing Cross Venous Ulcer Questionnaire (week 0, 6, 12)
- Wound status check [healed, not healed, recurrence] and any incidences of adverse events (week 18)
- Patient withdrawal rates due to change in management (e.g. need for surgery)
- Wound infection rates, any other adverse events
- Patient experience and satisfaction with the Granulox product and treatment regime

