6.1.1 Randomisation

Following written consent at -2 weeks, participants will be observed for two weeks to establish healing rate. At the end of two weeks, patients are only eligible for the intervention phase if their wound has healed <50% in the preceding two weeks. At this point, week 0, participants are allocated at random to the control or Granulox intervention group, using a randomised sequence from the freeware randomisation programme, see https://www.randomizer.org/. The randomisation is stratified for ulcer size, with PUSH score of 5 or less, and 6 or above as the cut-off. This size has been determined as the average size of a presenting foot ulcer previously (Zimny et al, 2002).

Sequential envelopes with each next randomisation allocation will be used to achieve concealment and these will be kept in the research department. The researcher will then inform the regular healthcare professional for the participant in question, and the participant themselves, which treatment they've been allocated to. The researcher will dispatch a Granulox canister to the clinic where the participant will be seen. At this stage the twice weekly treatment (though three applications per week would be allowed if dressing change is more than twice a week) will commence.

As the study involves administration of a spray it is not possible to achieve blinding for the participants nor the researchers – it is recognised that this increases the risk of bias.

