6.2.2 Exclusion criteria

- Under the age of 18 years
- Unable to fully understand the consent process and provide informed consent due to either language barriers or mental capacity
- Limited life expectancy, i.e. undergoing palliative care
- Active infection in foot ulcer that cannot be managed in podiatry service (ie requires specialist secondary care intervention)
- Any personal objection to being administered a product containing porcine material.
- Patients who are participating in another research study involving an investigational product.
- The patient has concurrent (medical) conditions that in the opinion of the investigator may compromise patient safety or study objectives, including alcohol or drug dependency.
- Foot ulcer in area of the foot, e.g. in between toes, which would make exact ulcer size measurement impossible.
- Patient pregnant, actively planning to become pregnant, or lactating
- Ankle brachial index < 0.6, measured within 3 months of baseline visit

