8. STATISTICAL CONSIDERATION AND DATA ANALYSIS PLAN

8.1 Analysis of baseline characteristics

To determine the demographics and characteristics of the patients in the two arms the following data will be collated:

- Age
- Gender
- BMI
- Smoking status
- Significant comorbidities, including peripheral arterial disease, heart failure, pretibial oedema.
- Aetiology and location of wound
- Presence of diabetes, and if so length of having condition
- Neuropathy
- Offloading of the foot ulcer
- Ankle-Brachial Index value (measured within last 3 months)
- Wound infection or not (or infected at any stage of participation)

Any differences in distribution will be established with Chi-squared test or ANOVA as indicated.

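### The protocol names wound infection incidence as a safety outcome, but its only infection analysis variable pools infection at entry with later infection and sits among the baseline characteristics

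*Protocol*

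**What the plan says.** Infection appears in four places in the protocol.

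- **Summary, secondary objectives.** The safety objective, running to 12 weeks, is specified as "Wound infection incidence; secondary interventions".
- **Section 5.6.2.** The outcome list has "Wound infection rates, any other adverse events". Most other outcomes in that list carry assessment weeks; this one does not.
- **Section 6.2.2.** The exclusion is limited to "Active infection in foot ulcer that cannot be managed in podiatry service (ie requires specialist secondary care intervention". An ulcer with a lesser infection is therefore eligible.
- **Section 8.1.** Among the baseline characteristics stands "Wound infection or not (or infected at any stage of participation". The section closes with "Any differences in distribution will be established with Chi-squared test or ANOVA as indicated".

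Section 8.3 lists the secondary outcomes to be compared between arms. It includes the Texas grading score but not infection. The Texas score is taken at weeks -2, 0, 3, 6, 9 and 12 in both arms (section 5.6.2). Its stages B and D denote infection, without and with ischaemia (Appendix 1).

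**The concern.** Incidence means new cases in people free of the condition at the start. Because infected ulcers may enter, incidence needs week-0 infection kept apart from later infection. The section 8.1 item does the reverse: one yes/no value covers infection at baseline and at any later time. Consent is at week -2 and allocation at week 0 (section 6.1.1), so the item can also take in infections from the run-in.

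Two things follow. First, a table meant to show that randomisation balanced the arms would contain events that happened after randomisation. An effect of treatment on infection would then appear there as a baseline imbalance. Second, if this item is used as the safety result, for want of any other infection variable, participants infected at entry count as cases in both arms whatever happens to them later. For a safety outcome this matters because it pulls a real difference toward no difference, and so can hide harm as well as benefit.

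**Working it through.** The protocol states no infection rate, entry prevalence or power for infection, so there is no figure to reproduce. All risks and prevalences below are assumptions. The 30 per arm is from the protocol summary.

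**1. Dilution.** Let p be the proportion infected at week 0, equal in expectation in both arms by randomisation, and r the risk of a new infection among the rest. The pooled variable counts

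p + (1 − p) × r.

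With r = 15% in one arm and 30% in the other (true ratio 0.50):

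| p | arm at 15% | arm at 30% | ratio |
|---|---|---|---|
| 10% | 0.10 + 0.90 × 0.15 = 23.5% | 0.10 + 0.90 × 0.30 = 37.0% | 0.64 |
| 20% | 0.20 + 0.80 × 0.15 = 32.0% | 0.20 + 0.80 × 0.30 = 44.0% | 0.73 |
| 30% | 0.30 + 0.70 × 0.15 = 40.5% | 0.30 + 0.70 × 0.30 = 51.0% | 0.79 |

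**2. No true difference.** With r = 15% in both arms, the pooled risks are 23.5%, 32.0% and 40.5% in each arm, and the ratio stays at 1.00. Pooling favours neither arm in expectation.

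**3. A harm scenario, and the price of restricting to those at risk.** Take r = 10% in control and 25% with Granulox (difference 0.15, ratio 2.5). The pooled difference is (1 − p) × 0.15. The at-risk set is 30 × (1 − p) per arm. Power is the two-sided 5% normal approximation Φ[(d − 1.96 × se0) / se1], where se0 uses the pooled proportion and se1 the separate ones.

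| p | pooled: difference / ratio | pooled: power, 30 per arm | at-risk set per arm | at-risk: power, difference 0.15, ratio 2.5 |
|---|---|---|---|---|
| 0 | 0.150 / 2.50 | 33% | 30 | 33% |
| 10% | 0.135 / 1.71 | 22% | 27 | 30% |
| 20% | 0.120 / 1.43 | 16% | 24 | 27% |
| 30% | 0.105 / 1.28 | 13% | 21 | 24% |

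Restricting to those free of infection at week 0 loses patients but less information than pooling does. Either way the power is too low for a test to settle the question.

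**4. What contact frequency could do.** Suppose true incidence is equal, an infection is detectable for L days, and it is noticed with probability min(1, L / gap between visits). Twice-weekly Granulox contact is a gap of 3.5 days. The control gap is not given, so it is varied:

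| L | control gap 3.5 days | 7 days | 14 days |
|---|---|---|---|
| 5 days | 1.0 | 5/5 ÷ 5/7 = 1.4 | 5/5 ÷ 5/14 = 2.8 |
| 7 days | 1.0 | 1.0 | 7/7 ÷ 7/14 = 2.0 |

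The entries are detection ratios, Granulox to control. They run from none to nearly threefold, depending on a gap that the protocol does not state.

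**5. What Texas staging every 21 days would catch.** 7/21 = 33% of 7-day episodes and 14/21 = 67% of 14-day episodes, equally in both arms. It does not repair unblinded scoring: with equal true risk, sensitivities of 0.9 and 0.7 in the two arms give 0.9/0.7 = 1.29, or 0.78 if reversed.

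**The case against.** The best defence is that the summary already says incidence, which ordinarily excludes infections present at entry, and that section 5.6.2 files infection with adverse events, where a pre-existing infection does not naturally belong. The exact at-risk set is commonly left to a statistical analysis plan, which may exist. This stands as far as silence is concerned: a missing definition of a new case would be no finding. It does not answer section 8.1, which is not silent. It states a pooled variable, and nothing elsewhere in the analysis section replaces it.

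Three stronger readings are tempting, and the protocol does not support them.

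- **That the comparison of infection between arms is biased.** Pooling leaves a null ratio at 1.00 and only dilutes a real one. Section 8.3 plans no comparison of infection, and the protocol has no decision rule that rests on it.
- **That the Granulox arm is watched more closely, so infections are two or three times as likely to be noticed there.** Section 5.2 says that grant-paid resource "means that there is sufficient capacity to treat study participants with the Granulox medical device", which hints at extra contact but gives no visit count. The spray goes on at redressing (section 1), and the third weekly application follows the dressing schedule: "though three applications per week would be allowed if dressing change is more than twice a week". Section 5.5 describes routine redressing for all patients, not for controls alone, and the control dressing frequency is not stated. Nor is detection proportional to contacts: with weekly control contact the ratio is 1.0 for a 7-day episode and 1.4 for a 5-day one. Unequal detection is a possible limitation, not an established fact.
- **That the Texas stage would cure the problem.** It separates existing from new infection and puts assessment on one schedule. But the treating podiatrists score it (section 5.2) and are told the allocation (section 6.1.1), and at three-week intervals it misses most short episodes. Section 6.1.1 already concedes that the lack of blinding raises the risk of bias.

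**Conclusion.** The point holds in a narrow form. The named safety outcome is incidence, infected ulcers may enter, and the one infection variable in the analysis section cannot measure incidence because it merges infection at entry with infection during the trial. Its place among the baseline characteristics also mixes an outcome into the balance check.

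The effect is dilution. On assumed risks of 15% and 30%, a true ratio of 0.50 appears as 0.64 to 0.79 at entry prevalences of 10% to 30%. On 10% and 25%, a true 2.5 appears as 1.71 to 1.28. The direction of the effect follows from the definition; its size depends wholly on how many ulcers are infected at week 0, which the protocol does not give. If none were infected at entry or during the run-in, there would be no dilution, though the variable would still be misplaced. The primary outcome is untouched.

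**What to change.** Split the section 8.1 variable.

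1. **Baseline:** infection at week 0, defined as Texas stage B or D, reported as a baseline characteristic.
2. **Safety outcome:** new infection after week 0 among participants at Texas stage A or C at week 0, by arm. Count a new stage B or D at weeks 3, 6, 9 or 12, and show alongside it the infections reported as adverse events between visits. Report descriptively with confidence intervals, given the low power.
3. **Separate list:** persistence of infection in those at stage B or D at week 0.
4. **Stated limitations:** assessment is unblinded, and contact frequency may differ between arms because the control dressing frequency is not given.

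The cost is a change of wording; the Texas stage is already collected at the same weeks in both arms. There are two downsides. The at-risk set is smaller: 24 per arm instead of 30 if 20% are infected at week 0. And three-weekly staging alone misses short episodes, which is why the Texas stage should not be the only infection endpoint and the adverse event reports must stay beside it.

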5.4 Recruitment

Participants will be randomised to either the control group (TaU) or the intervention group (TaU plus administration of Granulox spray) for 12 weeks or until ulcer healing has been achieved. All participants will have demographic data obtained and the following base line measures (table 2):

- Foot ulcer size measured with Convatec grid tool or equivalent measuring tool
- PUSH score (size and characteristics)
- Texas University grading scores.
- Mobility score (LifeSpace questionnaire)
- Quality of life assessment using
 - o EQ-5D-5L
 - o Cardiff Wound Impact Questionnaire
 - VAS pain scale

Table 3. Overview of measurements

Weeks	-2	0	3	6*	9*	12#	18#
· Ulcar size (Converted grid))	X	Х	X	X	X	X	110-11
PUSH score	Χ	Χ	Χ	Χ	X	Χ	A48.400401-144.1
Tiexas Universading score	X	1X	X	: X	\mathbf{X}_{i}	X	
Wound healed status		Χ	Χ	Х	X	Χ	Χ
Lifte Space Questilonnaire		X		X -		X 14 3	
QoL EQ-5D-5L		Χ		Χ	The state of the s	Χ	
QoL CWIQ ************************************	Angel bir sho	1 X 1	orași d	14X1		· XD a	
VAS pain scale	X	Χ	Χ	Χ	Χ	Χ	
Patient experience questionnaire	richt sach Richer Ha d	26021	dylast.	Brutta.		X [®]	

^{*} Allowed to be up to 1 week early or late

[#] Allowed to be up to 2 weeks early or late

@Granulox arm participants only

The Pressure Ulcer Scale for Healing (PUSH) tool, see Appendix 1 is a standardised method of assessing and monitoring the severity and healing of both pressure ulcers and venous leg ulcers (Stotts et al, 2001; Ratliff & Rodeheaver 2005). The Pressure Ulcer Scale for Healing (PUSH) is a valid, responsive, evaluative tool to monitor and document wound progress of foot ulcers (Hon, 2010). Findings also suggest that total PUSH scores predict time-to-heal for foot ulcers (Gardner 2011).

A mobility measure will be taken using a life space questionnaire, see Appendix 1 (Stalvey *et al* 1999). This is a tool that has demonstrated reliability and construct and criterion validity in establishing the spatial extent of an older person's mobility within their home setting. There are other versions (Peel *et al* 2005) that additionally measure the use of aids and equipment however this is not of particular interest within the study, hence the simpler version will be used.

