A recent review of specific health related quality of life instruments for venous leg ulcers favours the Charing Cross Venous Leg Ulcer Questionnaire (Appendix 2) (Smith *et al* 2010) above others such as the Hyland for its disease specific psychometric characteristics (Gonzalez & Verdu 2011).

5.5 **Follow-up**

Patients are in the study for a period of 18 weeks. Thereafter, the patient will be followed up as they would be in normal clinical practice. During and after the trial, clinical staff will redress the wound as per routine care, and during the trial they will conduct the measurement of the foot ulcer (grid measurement tool, Texas Univ grading and PUSH score). The researcher will be in attendance at -2 weeks, 0 weeks, and weeks 3,6,9,12 of study participation to randomise the patient, issue the Granulox spray if indicated, and conduct/collect the study participant questionnaires. The researcher will phone the participant at week 18 to check on wound status and any adverse event reporting.

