8.2 Primary outcome statistics

The primary objective for this trial is the healing rate of the foot ulcers, as assessed by tracing the wound using a Convatec measuring grid, or an equivalent measuring grid tool.

Confidential – This document and the information contained herein may not be reproduced, used or disclosed without written permission from Cumbria Partnership NHS Foundation Trust Page | 17

The average difference between time points will be calculated per group, 12 weeks being the primary endpoint but weeks 3, 6 and 9 will also be analysed. To compare the groups, the Mann-Whitney U-test will be applied.

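### With first visits continuing to 31 January 2019, week-18 follow-up runs to June or July 2019, so it cannot be complete, nor the final data analysed, in April 2019

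*Protocol*

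**What the plan says.** The Planned timeline in the protocol summary gives "Recruitment end date (last patient, first visit): 31 Jan 2019" and "Trial end date: Apr 2019". Table 2 in section 5.1 agrees: recruitment finishes in January 2019, follow-up is complete and data are analysed in April, and the manuscript and report are finished in May.

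The visit schedule is set elsewhere:

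- Section 6.1.1 puts consent two weeks before randomisation: "Following written consent at -2 weeks, participants will be observed for two weeks to establish healing rate". It continues: "At this point, week 0, participants are allocated at random to the control or Granulox intervention group".
- Section 8.2 fixes the main time point: "12 weeks being the primary endpoint but weeks 3, 6 and 9 will also be analysed".
- Section 5.5 sets the length of participation, "Patients are in the study for a period of 18 weeks", and the last contact: "The researcher will phone the participant at week 18 to check on wound status and any adverse event reporting".
- The footnote to Table 3 in section 5.4 gives the window for both week 12 and week 18: "Allowed to be up to 2 weeks early or late".

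Week-18 wound status (healed, not healed or recurrent) appears among the secondary objectives in the summary. Section 5.6.2 lists it as a secondary outcome together with adverse events at that time.

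**The concern.** The dates and the visit schedule cannot both be followed for patients who enter late. From 31 January to 30 April 2019 is under 13 weeks, while the schedule needs 20 weeks from first visit to last contact.

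If the stated end date governs, the loss is confined to the latest entrants. They would have no week-18 record of recurrence or adverse events, and their week-12 measurement would come under time pressure. If the schedule governs, an analysis in April, and a report finished in May, would come before the last patients' follow-up is complete. The protocol does not say which takes precedence.

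**Working it through.** **Inputs.** Last first visit 31 January 2019 and trial end April 2019, read as 30 April at the latest (summary); run-in of 2 weeks (section 6.1.1); primary time point at week 12 (section 8.2); last contact at week 18 (section 5.5); window of 2 weeks either side at weeks 12 and 18 (Table 3). Recruitment starts in July 2017 according to the summary and in August 2017 according to Table 2.

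**The plan's own figure.** Available time is 28 + 31 + 30 = 89 days, or 12.7 weeks. Required time is 2 + 18 = 20 weeks, or 140 days. The April date is not reproduced; the shortfall at nominal timing is 140 - 89 = 51 days.

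**Dates for the last entrant, with the first visit at week -2.**

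- Week 0 = 31 January + 14 days = 14 February 2019.
- Week 12 = week 0 + 84 days = 9 May 2019, window 25 April to 23 May.
- Week 18 = week 0 + 126 days = 20 June 2019, window 6 June to 4 July.

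**Most favourable reading.** Suppose the first visit in the summary means week 0, which also corresponds to counting the 18 weeks of section 5.5 from that visit. Week 18 is then 31 January + 126 days = 6 June, and two weeks early is 23 May 2019. That is still after April. On this reading the nominal week 12 is 25 April.

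**Latest first visit (week -2) compatible with 30 April 2019.**

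- Week 18, full early window: 30 April - 126 days = 25 December 2018.
- Week 18, nominal: 30 April - 140 days = 11 December 2018.
- Week 18, full late window: 30 April - 154 days = 27 November 2018.
- Week 12, nominal: 30 April - 98 days = 22 January 2019.
- Week 12, full early window: 30 April - 84 days = 5 February 2019, which is after recruitment closes.

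**Participants affected if April were enforced, assuming even accrual to 60.** From 1 August 2017 to 31 January 2019 is 548 days; from 1 July 2017 it is 579.

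- Week 18, early window: the last 37 days. 60 × 37/548 = 4.1 (60 × 37/579 = 3.8).
- Week 18, nominal: the last 51 days. 60 × 51/548 = 5.6 (60 × 51/579 = 5.3).
- Week 12, nominal: the last 9 days. 60 × 9/548 = 1.0.
- Week 12, early window: none.

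**The case against.** The strongest reply is that these are planning dates. The summary calls them planned and Table 2 calls them anticipated; nothing in the protocol stops follow-up when the end date arrives, and sections 5.4 to 5.6 positively require the week-12 and week-18 assessments. Staff who follow the schedule would simply continue past April, and no data would be lost. This stands to the extent that the data loss is conditional on the date being enforced. It does not remove the contradiction, because Table 2 expressly has follow-up complete and data under analysis in April.

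A second reply is that the visit windows give some slack. For week 12 that is correct: the last entrant's window opens on 25 April. For week 18 it does not help, since even the most favourable reading gives 23 May.

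A reader might go further and infer that the last entrants are bound to lose the primary endpoint. The documents do not support that, because the permitted early window brings every entrant's week-12 visit inside April. The price is measurement at about week 10 for someone entering on 31 January, on an outcome defined at 12 weeks. A reader might also infer that the timeline damages the trial's power. The date conflict changes neither the sample size, the significance level nor the test. At nominal timing it puts about one week-12 measurement at risk.

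**Conclusion.** The point holds for week 18 on every reading of the schedule: the last contact is nominally 20 June 2019, can run to 4 July, and is no earlier than 23 May. The April 2019 date for trial end, complete follow-up and analysis is therefore wrong as written. For week 12 there is only a risk: the nominal date of 9 May is after April, but the window reaches back to 25 April.

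If April were enforced, about 4 (early window) to 5-6 (nominal timing) of 60 participants would lack week-18 recurrence and adverse event data. That count assumes even accrual, a close on 30 April, and that the 60 participants are spread over time as first visits are. Entry concentrated near the end would raise it. This is a timetable error with a bounded effect on secondary and safety data; it is not a flaw in the design or the analysis.

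**What to change.** In the summary's Planned timeline and in Table 2, move the trial end date and the start of final analysis to July 2019, after the last week-18 window closes on 4 July 2019. Move the May 2019 report entry in Table 2 accordingly.

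If April 2019 has to be kept, bring the last first visit forward to 27 November 2018 so that the full late window fits. A cut-off of 11 December 2018 covers nominal timing only: a call made two weeks late would then fall on 14 May 2019.

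The first option is a date change in the next amendment, with reporting about two to three months later and no effect on visits or sample size. The second shortens recruitment by 65 days (27 November 2018 to 31 January 2019).
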